5.1 Study Design and Methods

5.2 Overview

This will be randomized, placebo controlled, double blinded study

We plan to enroll fifty subjects with homozygous sickle cell disease (HbSS), sickle-thalassemia (Hb S-ß thalassemia), HbSC, HbSD, or HbSO^{Arab}, in order to have 40 subjects complete at least 8 weeks of treatment, after an expected 20% dropout.

Subjects will receive 2% topical sodium nitrite cream twice a week for 10 weeks or placebo with vehicle only.

Subjects will have 0.1 cm of 2% sodium nitrite cream or placebo cream applied per 1 cm² of the total ulcerated area. If a subject has more than one ulcer, all of them will be treated with either "study cream" or placebo. Areas will be rounded to the nearest 1 cm². If a subject has more than one ulcer and the total sum of all of them is above 100 cm², then one of the ulcers can be enrolled

PI: [name]

^{*} If a patient does not qualify because he/she has an infection at the time of enrollment or at run-in, he/she can initiate the protocol two weeks after the infection has been cleared.

in the study, as long as it does not exceed the 100 cm² size. The other wounds will continue standard of care only. The total amount of sodium nitrite administered to each subject will vary depending upon the size of the ulcer but the treated total surface area will not exceed 100 cm² (i.e., subjects will receive a maximum of 10 cm of sodium nitrite cream).

Administration of study cream or placebo will be double blinded. The pharmacist will not be blinded, so he/she will be aware of who is receiving the investigational drug for safety purposes.

Randomization:

Randomization will be stratified by use of hydroxyurea to minimize its potential confounding effect on the study outcomes; we expect that 50% of participants use hydroxyurea. In addition, within each stratum (use or non-use), random treatment assignment will be balanced, i.e., 1:1 allocation, within blocks. This type of stratified block-randomized allocations will be generated by the study statistician applying a computer algorithm. The randomized allocation will occur once a subject is determined to be eligible for participation after the screening visit and the run in phase, but prior to the first cream application.

Un-blinding Procedures:

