The medical monitor may request unblinding to attribute toxicities if a serious adverse event occurs to determine attribution, or if a dose limiting toxicity occurs to determine if placebo or active treatment was used.

A run in period of at least 2 weeks will be conducted, during which patients will receive/optimize wound care at the Center that will enroll the subjects, following standard of care, routinely available therapies. Patients that experience a reduction of their wound size by >25% during this time will be excluded from the trial, as this suggests an effect secondary to improved wound care only. These patients will remain on protocol and their wound will be measured monthly for up to 6 months or until closure, whichever comes first. If a subject develops an acute vaso-occlusive episode and is hospitalized during the run in period, he/she will have the run in period extended in order to allow the subject to be safely discharged from the hospital and return to outpatient care.

Close monitoring of VSS, especially BP, will be done, to assess changes in patients receiving study cream, compared to placebo.

Measurements of all leg ulcers and photographs will be obtained at the following points: At Baseline

After the 2 weeks run in period, to determine eligibility for study cream application
At mid-point: after 10 applications of study cream, to determine the need for drug modification
At end of study: after the last application of the study cream

An accurate assessment of pain will be obtained each time that size measurements are obtained.

Quality of life questionnaire (ASCQ-Me) will be given before initial application and at the end of protocol or when the ulcer(s) is (are) healed, whatever comes first.

We will monitor metHb level as a safety measure, despite the fact that the phase 1 study did not show significant elevations of metHb. **Teratogenicity** is not a consideration, since the phase 1 study demonstrated minimal systemic absorption of nitrite and nitrate, therefore the risk for the gonads and potential offspring is limited to nonexistent.

Among the entry studies to be obtained, a **3-4 mm skin optional biopsy** may be performed at the edge of the ulcerated area. If the patient has multiple ulcers, the surgeon/wound care expert will decide which one is the safest to biopsy. This will be done

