PI: [name] Version 5 in order to assess cutaneous vascularization (i.e., angiogenesis), inflammation (tissue II-6, TGF- \Box , etc.), and markers of neurogenic inflammation³⁶.

At the end of 10 weeks of treatment, subjects that still have an open ulcer will be offered continuation of care at Montefiore or University of Pittsburg or referred back to the community.

Subjects will be followed off treatment but on study with monthly visits for an additional six months to evaluate the long term effect of topical sodium nitrite on the host and the ulcer (how many ulcers re-open or close). These visits will consist of measurement of all wounds by light photography and a detailed history of intervening ulcer treatments. If patients cannot return to the hospital or have moved away, we will call them and obtain the information on the phone and ask for a photograph. The photo can be obtained by the patient him or herself. Thereafter, they will be followed up with phone calls once a year for a total of 2 years, to establish whether this therapy is changing the natural history of ulcers in this population.

Rationale for the selection of subjects' number and endpoints

Sample size: We plan to randomize a total of 50 subjects to sample size of 20 completers per arm (40 subjects total) after an anticipated 20% dropout rate is taken into account. This sample size is determined based on feasibility of recruitment within the budget constraint and time frame of the study; we anticipate enrolling 1~2 eligible subjects per month. Although the focus of analysis will be more on estimation of treatment effect sizes and their 95% confidence intervals, the anticipated sample size is adequate to detect 88% vs. 48% response rate, as defined by >25% reduction of ulcer size from baseline, between treatment and control groups, with >80% at a two-sided significance level of 0.05 (see table 1). We note that in the Phase 1 study we observed an 88% response rate. Therefore, our study will be adequately powered if response rate in the placebo group is smaller than 48%.

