5.3 Recruitment

Potential subjects will be identified from the more than 800 patients in the Sickle Celldatabase at Montefiore Medical Center and the ~300 at the University of Pittsburgh. Referrals will be solicited from the New York Metropolitan area and Pennsylvania. We anticipate enrolling 35 subjects at Montefiore and 5 in Pittsburg. [name] has initiated a multidisciplinary SCD/wound care clinic at Montefiore, in collaboration with [name], an associate investigator in this study and a wound expert, which sees about 4 patients per week and draws referrals from many of New York Hospitals. Entry into the study will begin when the subject meets all inclusion criteria and signs an informed consent document to confirm their willingness to participate.

Screening: The subjects will be initially evaluated during a routine clinical visit to determine eligibility, obtain informed consent, have a detailed medical history and physical examination, and have clinical labs that include a hemoglobin electrophoresis for genotype confirmation, unless one is available in the chart within the previous 3 months. Potential subjects will have a detailed assessment of all of their wounds. Methemoglobin level will be drawn to exclude congenital methemoglobinemia. As methemoglobin levels vary with the state of oxygenation and the severity of the anemia and hemolysis, patients who have at least two documented metHb levels below the 3.5% threshold will continue the study even if the meth Hb levels rise above 3.5% during the weeks leading to the first application, as long as they remain below 4.5%. A pregnancy test will be performed for women in reproductive age.

The subject that is deemed eligible will then be scheduled for routine wound care, as determined by the WONC and the PI, of two weeks' time, called the "Run In Period". At the end of the two weeks, the ulcer areas will be measured. Patients whose ulcer total surface area decreases by >25% at the end of the run in period will be excluded from the therapeutic portion

PI: [name]

of the trial.

Standard of care for wounds includes the following:

- Cleanse leg with skin cleanser
- Cleanse ulcer with normal saline & gauze removing any debris from woundbed.
- Apply petrolatum-based ointment around the edge of the wound
- Cover ulcer with non-adhering foam pad if the ulcer size is < 2cm²
- Cover ulcer with Calcium Alginate dressing if the ulcer size is > 2cm²

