8.1 Primary Endpoints and Analysis

The primary endpoint of this phase II study will be the assessment of tolerability and occurrence of adverse effects of topical sodium nitrite compared to placebo.

- 8.1.1 Frequency of each adverse event will also be tabulated. To compare the safety of prolonged (10 weeks) treatments between the experimental/treatment and usual care/placebo groups, we will apply a non-parametric Mann-Whitney test on the number of adverse events.
- 8.1.2 Effect sizes of the treatment on the ulcer size reduction will be determined by differences in response rates or odds-ratios, and the 95% Cl's will accordingly be To test if topical sodium nitrite accelerates wound healing, as defined by >25% improvement over placebo arm, we will apply a Chi-square test. Logistic regression models will be applied if inclusion of confounding variables deems necessary. We will also test if declines of weeklymeasured absolute ulcer size on a continuous scale over the study period will be different between the two groups by applying mixed effects linear models for analysis of repeatedmeasure outcomes.
- 8.1.3 Effect sizes of the treatment on the pain reduction will be determined by differences in response rates or odds-ratios, and the 95% CI's will accordingly be estimated. To test if topical sodium nitrite decreases pain at the wound site >20% over placebo, we will apply a Chisquare test. Logistic regression models will be applied if inclusion of confounding variables deems necessary. We will also test if declines of weekly-measured absolute pain VAS scores on a continuous scale over the study period will be different between the two groups by applying mixed effects linear models for analysis of repeated-measure outcomes.

25

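### Standard-care healers can pass the run-in and erode the stated power, and the run-in healing trend measured before randomisation is not prespecified as a covariate

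*Combined protocol and SAP*

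**What the plan says.** Under Section 5.2 Overview, "A run in period of at least 2 weeks will be conducted", with optimised standard wound care. The exclusion rule follows: "Patients that experience a reduction of their wound size by >25% during this time will be excluded from the trial". The stated reason is that such shrinkage points to better wound care alone. Section 5.3 Recruitment repeats the rule for total ulcer area: "Patients whose ulcer total surface area decreases by >25% at the end of the run in period will be excluded from the therapeutic portion". Area is measured at baseline and again after the run-in, and randomisation comes after that.

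The sample-size paragraph of Section 5.2 bases power on response, "as defined by >25% reduction of ulcer size from baseline". Treatment lasts 10 weeks, and the last area measurement follows the last application. With 20 completers per arm, the plan claims more than 80% power for 88% against 48% response at two-sided 0.05. It adds that "our study will be adequately powered if response rate in the placebo group is smaller than 48" percent.

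Section 8.1.2 tests healing response with a chi-square test and continues: "Logistic regression models will be applied if inclusion of confounding variables deems necessary". The opening of Section 8 adds to multivariable models those variables found unequally distributed between arms. A mixed model of weekly absolute ulcer size is also planned. Run-in change is named in none of these, and randomisation is stratified by hydroxyurea use only.

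**The concern.** The run-in is there to take out healing that better wound care alone would produce. It applies the responder threshold over about one fifth of the response period, so it catches only very fast healers. Slower ones are randomised and may respond on either arm without any drug effect. That raises the placebo rate, and the power claim depends on that rate staying below 48%.

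The run-in also gives each randomised subject a measured healing trend before allocation. If the trend predicts outcome, adjusting for it improves precision whether or not the arms differ on it. A rule that adds covariates only when they look unbalanced misses that benefit and leaves the model to be chosen after the data are seen. With 40 completers fixed by feasibility and budget, this is one of the few ways to gain precision at almost no cost.

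**Working it through.** **Inputs from the documents.** Run-in cut 25% over at least 2 weeks, response cut 25%, treatment 10 weeks, 20 completers per arm, 88% against 48%, two-sided 0.05 (all Section 5.2); unadjusted chi-square (Section 8.1.2). The 10-week horizon for response is inferred from the treatment length and the end-of-study measurement, because the responder definition names no time point.

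**Step 1: the plan's own figure.** The pooled normal formula with n = 20 per arm, 0.88 and 0.48 gives power 0.797. Exact binomial enumeration of the uncorrected chi-square gives 0.821. The stated figure of more than 80% therefore reproduces for the named test.

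**Step 2: the two thresholds on one time scale.** For a constant proportional 2-week shrinkage r, 10-week shrinkage is 1 − (1 − r)^5.

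- 25% over 10 weeks corresponds to r = 1 − 0.75^(1/5) = 5.6% per 2 weeks. A linear course gives 25%/5 = 5.0%.
- r = 10% gives 41% at 10 weeks, 15% gives 56%, and 20% gives 67%.
- r = 25%, the run-in limit, gives 1 − 0.75^5 = 76%.

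The run-in thus admits the whole band from about 6% to 25%, all of it on course to respond.

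**Step 3: power as the placebo rate rises** (active fixed at 88%, 20 per arm):

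| Placebo response | Pooled formula | Exact chi-square |
|---|---|---|
| 40% | 0.92 | 0.93 |
| 48% | 0.80 | 0.82 |
| 50% | 0.76 | 0.78 |
| 55% | 0.65 | 0.68 |
| 60% | 0.53 | 0.55 |
| 65% | 0.40 | 0.41 |

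**Step 4: how many such healers would matter.** Suppose a share f of those randomised respond on standard care anyway and the rest respond on placebo at 30%. Both values are assumptions. The placebo rate is f + (1 − f) × 0.30:

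- f = 0.2: 44%, power 0.87 (pooled formula)
- f = 0.3: 51%, power 0.74
- f = 0.4: 58%, power 0.58

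**Step 5: what the covariate could return.** An illustrative simulation, with all variances assumed, added run-in change to a logistic model. Power moved as follows:

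- from 80% to 81% at a run-in/outcome correlation of 0.14;
- from 81% to 87% at 0.45;
- from 82% to 92% at 0.62.

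Type I error was 5–6%, rising to 7–8% when the correlation was very high.

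**Step 6: baseline.** The schedule of assessments puts the Baseline visit at about week −2, before the run-in, and the responder definition does not say which measurement it uses. If it is that visit, a subject who shrank 20% in the run-in needs only a further 1 − 0.75/0.80 = 6.25% on treatment to count as a responder.

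**Step 7: sparse data.** At the planned rates, expected non-responders are 20 × 0.12 = 2.4 on active and 20 × 0.52 = 10.4 on placebo. All 20 active subjects respond with probability 0.88^20 = 7.8%, and an ordinary logistic treatment estimate is then infinite.

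**The case against.** The strongest reply is that nothing here is an error. The plan says only that shrinkage above 25% suggests a wound-care effect; it does not claim that everyone below the cut is free of one. Remaining standard-care healing is what a concurrent, blinded, randomised placebo arm is for. A reader might infer from the mismatched periods that the comparison is biased. The documents do not support that, because such healers are expected equally in both arms. This part of the reply stands.

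The plan also discloses its dependence on the 48% rate, says that feasibility set the sample size, stresses estimation with 95% confidence intervals, and names tolerability and adverse effects as the primary endpoint. That stands too, although healing sits under the same heading and carries the only power statement. A reader might infer that placebo response will exceed 48%; the documents contain no placebo data either way.

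Constant healing is doubtful. In the phase 1 Table 1 (a 4-week study), cohort 2 had shrunk 15.8% at week 3. A constant rate predicts 20% at week 4, and 3.8% was observed, with one subject progressing. Cohort 1 went from 29.9% to 28.8% against 38% predicted. The three higher-concentration cohorts kept shrinking. The cohorts were small and all treated, but they caution against routine extrapolation from 2 weeks to 10.

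The prognostic strength is likewise assumed. Measuring response from the end of the run-in puts error in that area into covariate and outcome with opposite sign. In one illustrative check (10% measurement error, slope correlation 0.5), the run-in/outcome correlation was 0.14 with that baseline, against 0.40 with the pre-run-in baseline.

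Finally, it would be too strong to say that the plan can never use the run-in trend: the imbalance rule in Section 8 could bring it in. The accurate statement is that it is not prespecified.

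**Conclusion.** The point holds as one of power and precision, not of bias. The run-in lets through ulcers shrinking about 6–25% on standard care. On a constant proportional course these would respond without drug, and enough of them would take placebo response past 48%. The cost is then steep: exact power falls from 82% to 68% at 55% and to 55% at 60%. How many such subjects will be randomised is not known from the documents.

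The threshold mismatch is not itself a mistake and need not change; a covariate removes no healers and leaves the placebo rate as it is. What can be improved is the analysis. A value known before randomisation should be prespecified rather than left to an imbalance check. The expected gain runs from nil at weak correlation to roughly 5–10 power points at correlations of 0.45–0.6, under assumed variances. It also depends on a baseline that the plan does not yet define. In the simulation, adjustment lost no power at weak correlation, which makes prespecification reasonable despite the uncertainty.

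**What to change.** Keep both thresholds and make these changes:

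- **Baseline (Section 8.1.2).** Define it for response as the area at the end of the run-in, before the first application.
- **Covariate (Section 8.1.2).** Prespecify the log ratio of end-of-run-in to Visit 1 area, divided by weeks of run-in because its length can vary. Include it in the healing logistic model and the repeated-measures ulcer model, whatever the observed balance. In the latter, add its interaction with time, since the treatment contrast is a difference in decline.
- **Estimation (Section 8.1.2).** Report the standardised risk difference with its 95% CI from a penalised (Firth) fit, because separation is possible. Take the p-value from a permutation test, because the likelihood-ratio test is slightly anti-conservative at 40 subjects.
- **Power (Section 5.2).** Show power at placebo response rates of 50–65%: exact chi-square values are 78%, 68%, 55% and 41% at 50%, 55%, 60% and 65%.

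The cost is wording in the analysis and sample-size sections. No visit, measurement or eligibility rule changes, and the data are already collected. The analysis becomes slightly more complex, and the power statement looks less favourable above 48%.

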> experienced a decrease in leg ulcer surface area, fig 1 (pretreatment 4.65 vs. post-treatment 2.78 cm^2 , p < 0.001), and improvement in pain scores at the ulcer site (pretreatment VAS score of 4.87 vs. post treatment of 2.91, p=0.024). Changes in pain score were not statistically significant at the ulcers that were not treated with study cream, p=0.96 (50% of subjects had more than one ulcer and only one was treated with study cream). Healing was dependent on sodium nitrite concentration, and it was most marked in cohort 4 (2.0%), the one treated with the highest strength of sodium nitrite cream, with 2 of 3 subjects experiencing complete closure of the ulcer (89% decrease in surface area), then cohort 3a (1.8%), with a 68.5% healing rate and

[figure not shown]

Figure 1: Changes in leg ulcer surface area before and after application of sodium nitrite cream (A) Wound size measured by digital planimetry. (B) Wound sizes measured manually (longest length and widest width). (C) Changes in wound size according to sodium nitrite concentration. Arrows in (A) and (B) represent first application of cream. Plotted points or bars are mean values and error bars are standard error of the mean. *p=0.0058 compared with first application. †p<0.0001. ‡p=0.0001. §p=0.0008. from Lancet Haematology 1, e95-e103. PMC4415859 (Figure 1, PI is first author)

one out of 4 experiencing complete closure, then cohorts 1, 2 and 3 with healing rates of 29, 3.8 and 33%, respectively. See Table 1 below.

11

PI: [name] Version 5

Table 1 : Percent of ulcer's surface healed from beginning of therapy								
Cohort/concentration	Week 3	End of study						
1/0.5%	29.9%	28.8%						
2/1.0%	15.8%	3.8% (one subject progressed)						
3/1.5 %	22.5%	32.9%						
3a/1.8%	56.0%	68.5% (one of four ulcers closed completely)						
4/2.0%	55.1%	88.6% (two of three ulcers closed completely)						

Application of topical sodium nitrite was associated with a significant increase in periwound cutaneous blood flow measured by laser speckle contrast imaging and increased periwound skin temperature by infrared thermography (fig 3).

[figure not shown]

Figure 2 legend: Top panels: Laser speckle analysis of blood flow before (A) and after (B) application of sodium nitrite

 $\textbf{Lower panels: } Infrared \ photography \ of \ an \ individual \ subject \ before \ application \ (C) \ of \ topical \ baseline) \ and \ immediately \ after \ (D).$

[figure not shown]

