3.0 Specific Aims

Hypotheses:

- •Topical sodium nitrite cream, at 2% concentration, is safe and well tolerated when applied for an extended period of time (10 weeks) in patients with sickle cell disease and leg ulcers.
- •Topical sodium nitrite accelerates healing of skin ulcers and decreases ulcer relatedpain compared to placebo in patients with sickle cell disease and leg ulcers.

Specific Aims:

- To determine the safety and tolerability of prolonged (10 weeks), twice a week application of topical sodium nitrite in patients with sickle cell disease and leg ulcers
- To determine if topical sodium nitrite accelerates wound healing as defined by >25% improvement over placebo arm
- •To determine if topical sodium nitrite decreases pain at the wound site >20% over placebo

Secondary Objectives:

- To evaluate the effect of hydroxyurea on leg ulcer's healing in combination with topical sodium nitrite or placebo
- To assess changes in ulcer microbiome after application of sodium nitriteor placebo and how they may relate to rate of healing
- •To evaluate the dermal composition and microvascular structure in the ulcer's biopsy of subjects enrolled on this study.

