4.1 Inclusion and Exclusion Criteria

4.2 Eligibility

Subjects must be at least 18 years of age and have provided informed, written consent for participation in this study.

Each subject must meet all of the following inclusion criteria during the screening process in order to participate in the study:

- Subjects must have a diagnosis of sickle cell disease (SS, SC, Sß-thalassemia, SD, SOArab).
- Have one or more ulcers in one or both legs and/orfeet.

- •Leg ulcers that will receive treatment must be no larger than 100 cm².
- •No history of congenital methemoglobinemia.
- •Have documented normal G6PD activity.

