Rationale for end point of decrease in ulcer size: A decrease of 25% from baseline was used as a significant end point in Perrine's study of arginine butyrate in SCD leg ulcers³⁷. The FDA's own guidelines for research in cutaneous ulcers and burns specify: "Measurement of partial wound healing in early phase clinical trials, if prospectively defined, may indicate relevant biological activity and help guide subsequent trial design". Therefore, since this is a phase II trial, I think it is prudent to be conservative and reserve the complete closure end point for the phase III trial. Recently [name] and other dermatologists have challenged the idea of complete closure as the only end point for skin ulceration as being counterproductive for the development of new therapies, and significantly different from standards used in cancer trials, where a 10-20% response rate is often sufficient to claim success of a drug ordevice³⁸.

Pain threshold: A decrease of 20% was selected based on the accepted change of pain of **minimum 2 point** decrease on the VAS scale being considered as significant in clinical end point in research settings³⁹. The VAS scale ranges from 0-10, so 20% change is 2 points. Moreover, the finding of improvement in pain at the treated ulcer site was very interesting and needs further investigation.

In the phase 1 study⁴⁰ we conducted, we observed an increase in blood flow in the skin of individuals with chronic ulceration compared to an area that was not ulcerated. The lack of controls without ulcers prevented us from concluding that the high blood flow had a causative effect on the ulcer formation and delayed healing. Furthermore, it was not clear whether the high blood flow observed at baseline, i.e., before cream application, was different than what we would expect in patients with SCD.

Secondary end points were chosen in order to further our knowledge of the etiology of poor healing in SCD ulcers, based on the results from the prior study.

19

PI: [name] Version 5

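### The pain threshold is justified as a 2-point fall on the 0-10 VAS, but the aims and the test carry forward only a 20% figure with no stated base

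*Combined protocol and SAP*

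**What the plan says.** The rationale is in section 5.2, under the pain threshold. It opens "A decrease of 20% was selected based on the accepted change of pain of" at least 2 points, such a fall being a "decrease on the VAS scale being considered as significant in clinical end point in research settings". It then gives the conversion: "The VAS scale ranges from 0-10, so 20% change is 2 points".

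The aim in section 3.0 reads "To determine if topical sodium nitrite decreases pain at the wound site >20% over placebo", and the Precis has the same aim. The analysis in section 8.1.3 reads "To test if topical sodium nitrite decreases pain at the wound site >20% over placebo, we will apply a Chisquare test". It expresses the effect as a difference in response rates or an odds ratio. The same section also plans a mixed model on weekly absolute VAS scores.

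The 2-point figure appears in neither the aims nor section 8.1.3. By contrast, section 5.2 defines the ulcer-size responder explicitly as a reduction of more than 25% relative to baseline.

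On entry, section 4.2 asks that subjects "Have one or more ulcers in one or both legs and"/or feet. Neither 4.2 nor 4.3 sets a minimum pain score. Section 5.3 has a separate VAS taken for each ulcer and does not say how several ulcers combine into one result per subject.

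**The concern.** A chi-square test on response rates needs a rule that classes each subject as responder or non-responder. For pain no such rule is written out. The reader has a percentage without a base in the aims and the test, and an absolute number of points in the rationale. These agree only if the percentage is taken of the full scale.

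Two things are at stake:

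- If the percentage is applied to each subject's own baseline, as the ulcer-size rule is, falls well short of the justified 2 points count as success.
- If the 2-point rule is applied, subjects with little pain at entry are fixed non-responders in both arms.

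Pain relief is a stated aim, and the Precis says the trial should supply the effect size for phase III. With 20 completers planned per arm, reclassifying a few subjects moves the result, and an open rule can be settled after the data are seen.

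**Working it through.** **Inputs.** VAS range 0-10 and the 2-point minimum (section 5.2); phase 1 means, "pretreatment VAS score of 4.87 vs. post treatment of 2.91" (section 2.4); 20 completers per arm (section 5.2). The documents give no distribution of baseline VAS for this trial and no power figure for pain.

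**1. The plan's own figure.** 0.20 × 10 = 2.0 points. It is reproduced, with 20% taken of the scale range. On that base it is 2 points at every starting score.

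**2. The same 20% taken of the subject's baseline.** At 4.87: 0.20 × 4.87 = 0.97 points, and 0.974 / 2 = 0.49 of the justified fall. In general the ratio is (0.20 × baseline) / 2 = baseline / 10, so the two rules coincide only at a baseline of 10.

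| Baseline VAS | 20% of baseline (points) | 2 points as % of baseline |
|---|---|---|
| 1 | 0.2 | cannot be met |
| 2 | 0.4 | 100 |
| 3 | 0.6 | 67 |
| 4.87 | 0.97 | 41 |
| 8 | 1.6 | 25 |
| 10 | 2.0 | 20 |

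**3. A single subject with the phase 1 average change.** 4.87 − 2.91 = 1.96 points, and 1.96 / 4.87 = 40.2%. That subject responds on the percent-of-baseline rule (twice the threshold) and falls 0.04 points short on the 2-point rule.

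**4. Between-arm reading.** If the 20% is a difference between arms, it says nothing about which individual is a responder, and the rule needed for the chi-square test is missing altogether.

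**5. Low starting scores.** Below a baseline of 2, a 2-point fall is impossible. Read strictly as more than 2 points, it is also impossible at exactly 2. On the percent-of-baseline rule, a change from 1 to 0 is a 100% response. At a baseline of 0 neither rule can be met.

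**6. Dilution on the 2-point rule.** If a fraction f of each arm starts below 2, the observed difference is (1 − f) times the difference among those able to respond. Assuming f = 10% to 25% and a 30-point difference: 30 × 0.90 = 27 and 30 × 0.75 = 22.5 points. The loss of 3 to 7.5 points is 0.6 to 1.5 subjects out of 20.

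**7. Illustration of how far the two rules diverge.** Assumptions, none from the documents except the mean: baseline mean 4.87 with SD 2 to 3, SD of change 1.5 to 2.5, scores clipped to 0-10. By simulation, about 8-17% start below 2. Response rates are:

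| Mean fall | More than 20% of baseline | At least 2 points |
|---|---|---|
| 0 | 25-35% | 8-20% |
| 1.96 | 61-73% | 41-46% |

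**The case against.** The strongest reply is that section 5.2 already explains the number. The only rationale given is an absolute 2-point fall, converted through the scale range. Neither the aim nor the test mentions baseline, although the ulcer-size rule does. This has force: the documents' own explanation points to 2 points. A reader might infer that the plan has halved its threshold. The text does not support that; it supports only that the aims and section 8.1.3 leave the halved reading open.

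Four further limits stand:

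- A reader might infer that no reading tests a clinically relevant fall. That is wrong on the 2-point reading, which tests exactly the fall that section 5.2 justifies.
- The halved threshold and the unreachable threshold are alternatives, one per reading. They cannot both occur.
- The 4.87 is a group mean over 18 phase 1 subjects and five concentrations, so about half holds near that score and not for every subject.
- Low-pain subjects are randomised to both arms, so they dilute the difference without biasing it. The loss is small beside the imprecision: for assumed rates of 50% and 20% with 20 per arm, the 95% interval half-width is 1.96 × √(0.5 × 0.5/20 + 0.2 × 0.8/20) = 0.28, or 28 points.

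The plan also names tolerability and adverse effects as the primary endpoint, stresses estimation over testing, and has a VAS model that needs no threshold. What remains is that the 2-point rule does not reach the sections that govern the analysis, and that no pain responder is defined.

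**Conclusion.** The concern holds as an inconsistent and incomplete definition of pain response. The justified fall is 2 points. The aims and the test state a percentage without a base, which allows at least three readings. On the percent-of-baseline reading the threshold is 0.97 points at the phase 1 mean, 49% of the justified fall, and baseline/10 of it in general. On the 2-point reading, subjects starting below 2 cannot respond.

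The arithmetic rests only on figures in the protocol. The share of subjects with low starting scores, and the response rates in the illustration, rest on assumed spreads. The reach is limited to one binary comparison that has no stated power; the mixed model on absolute VAS is not affected. It should be corrected because the correction is nearly free and prevents the rule from being chosen once results are known.

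**What to change.** In the Precis and sections 3.0, 5.2 and 8.1.3:

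- Define pain response per subject as a fall of at least 2 points on the 0-10 VAS, from the Visit 3 value taken before application to the end-of-study value.
- Take it at one treated ulcer, chosen by a rule fixed before treatment, for example the treated ulcer with the highest Visit 3 VAS.
- Restate the aim and the test as a higher proportion with a fall of at least 2 points on sodium nitrite than on placebo, in place of the 20% wording.
- Keep all randomised subjects in the responder test, in line with the intent-to-treat commitment in section 8. Use the subset with Visit 3 VAS of at least 2 as a sensitivity analysis only.
- Adjust the VAS mixed model for the starting VAS and make it the main pain estimate, since it needs no threshold that low starting scores cannot reach.

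The cost is wording. VAS is already collected per ulcer with each application and at end of study. Section 5.3 should add that the Visit 3 score is taken before the cream, because it now gives no order. The downside is a lower response rate than under a percent-of-baseline rule.
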